## **4.2 Study Subjects**

### **4.2.1 Subject Disposition**

The number of subjects who were screened, failed screening, enrolled, received anticoagulant treatment, randomized along with the reason for not being randomized, and the number of subjects who received ciraparantag/PBO treatment will be presented. For each treatment group and overall, the number and percentage (of randomized subjects) who complete the study, and the number and percentage (or randomized subjects) who discontinue early from the study and the reason for discontinuation will be presented.

Eligibility status for the study will be listed for all screened subjects.

### **4.2.2 Protocol Deviations**

Protocol deviations will be identified prior to database lock and may include but are not limited to: significant violations of inclusion/exclusion criteria, noncompliance with the study treatment taken, the use of prohibited medications or not following clinical trial protocol procedures that may affect evaluation of the primary or secondary efficacy endpoints.

All protocol deviations will be listed by subject and summarized by deviation type and treatment group.

### **4.3 Subject Demographics and Other Baseline Characteristics**

Demographic and baseline characteristics will be summarized by each treatment and cohort for the Efficacy Population, and as applicable for the Anticoagulant Population. The demographic and baseline characteristics will consist of age, age group (18 to <50 years vs.  $\geq 50$  to 75 years; <65 years vs.  $\geq 65$  years), gender, race, ethnicity, height (cm), weight (kg), body mass index (BMI) ( $\text{kg}/\text{m}^2$ ), BL WBCT (seconds), WBCT on Day 4 pre-ciraparantag/PBO (seconds) and the percentage of BL (%). Counts and percentage of subjects with Day 4 pre-ciraparantag/PBO WBCT  $\geq 120\%$  of BL,  $\geq 130\%$  of BL,  $\geq 140\%$  of BL, and  $\geq 150\%$  of BL will also be tabulated. Individual demographic and baseline characteristics will be listed by subject.

The age is a calculated parameter. Age will be calculated using the subject's date of birth and the subject's informed consent date. Continuous variables (age, height, weight, BMI, BL WBCT, Day 4 pre-ciraparantag/PBO WBCT, and Day 4 pre-ciraparantag/PBO WBCT percentage of BL) will be summarized by n, mean, SD, min, median, and max. Number of subjects and percentages will be used to describe categorical variables (age group, gender, race, ethnicity and WBCT (as a percentage of BL) categories). No statistical hypothesis tests will be performed on these characteristics.

### **4.4 Medical/Surgical History and Procedures/Non-Drug Therapies**

The presence/absence of any current medical condition and/or other significant medical/surgical history will be coded using Medical Dictionary for Regulatory Activities (MedDRA) Version 20.0, or higher. Any procedures/non-drug therapies will also be coded using MedDRA or World Health Organization (WHO) Drug Enhanced Dictionary (March 2017 or later), as appropriate.

Medical/surgical history will be summarized by treatment and cohort, and listed by subject. Procedures/non-drug therapies will be summarized by treatment and cohort, and listed by subject.

### **4.5 Prior and Concomitant Medications**

All prescription medications and over-the-counter (OTC) products, including herbal products, taken within 14 days prior to Day 1 or during the study period will be documented in the subject's source documentation and the eCRF.

Details of all medications must be recorded at trial entry. Any changes in concomitant medications must be recorded at each visit. The information collected for each concomitant medication includes dosage, route, start date, stop date (or continuing) and indication. Prior medications will be recorded at the screening visit and will be defined as those medications with start prior to the first dose of anticoagulant on Day 1. Concomitant medications will be defined as those medications with a stop date after the

first dose of anticoagulant or with a missing stop date. Prior and concomitant medications will be coded using the World Health Organization (WHO) Drug Enhanced Dictionary (March 2017 or later).

Prior and concomitant medications will be summarized by treatment including Anatomical Therapeutic Chemical (ATC) classification level 3, preferred term and reported term. Medications will also be listed by subject.

## **4.6 Efficacy Analyses**

### **4.6.1 Primary Efficacy Endpoint**

The primary efficacy endpoint is achieving WBCT  $\leq 120\%$  of BL (as measured by coagulometer) within 1 hour after administration of ciraparantag/PBO which is subsequently sustained after 1 hour through at least 6 hours after ciraparantag/PBO dosing. The null hypothesis for this endpoint is that the true (success) proportions of subjects meeting the primary efficacy endpoint are equal for the two treatments, and the alternative hypothesis is that they are unequal. The statistical hypotheses are as follows:

$$H_0: \pi_1 = \pi_2$$

and

$$H_1: \pi_1 \neq \pi_2,$$

where  $\pi_1$  and  $\pi_2$  are the true success proportions for ciraparantag and PBO, respectively.

This endpoint will be summarized by cohort and treatment group (ciraparantag dose vs. PBO) using frequencies and percentages and an exact (Clopper-Pearson) 95% confidence interval (CI) for the true percentage based on the binomial distribution. The difference in percentages between treatments (ciraparantag dose vs. PBO) will be tested using Boschloo's test (Boschloo 1970). A 95% CI for the difference in percentages will be constructed by the Miettinen and Nurminen method (Newcombe 1998).

### **4.6.2 Secondary Efficacy Endpoints**

The first two secondary efficacy endpoints will be summarized by counts and percentages. No statistical analysis will be performed for the remaining secondary efficacy endpoints.

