#### **9.3.2.2. Secondary Efficacy Endpoint Analyses**

The secondary efficacy endpoints are as stated in Section [9.2.1.2](#). These endpoints will be analyzed in the same manner as the primary efficacy endpoint.

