### **3.4 Sample Size Justification**

Assuming true response rates for the primary efficacy endpoint of 78% and 5% in the first active dose group and the placebo group, respectively, 18 subjects with a 2:1 randomization ratio will have 91% power at 0.05 two-sided significance level based on the Boschloo's test. Assuming true response rates of 66% and 5% in the second active dose group and the placebo group, respectively, 12 subjects in each group will have 94% power. Note: For the second active dose group, the treatment allocation ratio will be 2:1 (ciraparantag:placebo), but placebo subjects will be pooled within each cohort, so the analyses will be comparisons of two groups of 12 subjects each.

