### **3.6 Handling of Missing Data**

For the primary efficacy endpoint, i.e. achieving a WBCT  $\leq 120\%$  of BL within 1 hour after administration of ciraparantag/PBO, which is subsequently sustained after 1 hour through at least 6 hours after ciraparantag/PBO dosing, the subject must have non-missing WBCT  $\leq 120\%$  of BL at all scheduled time points in the 1-6 hours assessment window to be a responder, otherwise the subject will be deemed a non-responder, including subjects with any missing data in this window. Missing data at time points earlier than 1 hour (i.e. 0.25 hour and 0.5 hour) will not affect the primary efficacy responder status determination. The secondary efficacy endpoints will be analyzed in the same manner. For the tertiary efficacy endpoints that evaluate responder status at each time point, a subject with a missing WBCT value will be considered as a non-responder for the specific time point.

For the other endpoints including the pharmacokinetic analysis, missing data will not be imputed.

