### **3.7 Adjustment for Multiple Comparison**

Each group in each cohort will be treated as a standalone sub-study and analyzed separately. Within each group in each cohort, if the primary efficacy endpoint is positive, i.e.,  $p\text{-value} < 0.05$ , the study will be declared positive, and we will test the secondary efficacy endpoints in three reversal target clusters in parallel as shown in [Table 5](#).

Because a goal of the study is to verify the dose and the endpoints for future evaluations of ciraparantag, we don't plan to control the multiplicity for the entire set of 8 secondary

endpoints. Instead, the testing approach controls the multiplicity for each reversal target cluster separately.

**Table 5: Hypothesis Testing Paradigm of The Secondary Efficacy Endpoints  
For Each Dose Group Within Each Cohort**

120% Reversal Target Cluster	115% Reversal Target Cluster	110% Reversal Target Cluster
Achieved within 30 minutes hour and subsequently sustained from 30 minutes to 6 hours	Achieved within 1 hour and subsequently sustained from 1 hour to 6 hours	Achieved within 1 hour and subsequently sustained from 1 hour to 6 hours
	if p-value <0.05 ↓	if p-value <0.05 ↓
	Achieved within 30 minutes and subsequently sustained from 30 minutes to 6 hours	Achieved within 30 minutes and subsequently sustained from 30 minutes to 6 hours
if p-value <0.05 ↓	if p-value <0.05 ↓	if p-value <0.05 ↓
Achieved within 15 minutes and subsequently sustained from 15 minutes to 6 hours	Achieved within 15 minutes and subsequently sustained from 15 minutes to 6 hours	Achieved within 15 minutes and subsequently sustained from 15 minutes to 6 hours

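### After lack of efficacy was seen, the SAP leaves six of eight secondary endpoints without a summary and two with bare counts, while Section 3.7 still states a rule to test all eight

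*SAP*

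**What the plan says.** Protocol 9.3.2.2 says of the eight secondary endpoints: "These endpoints will be analyzed in the same manner as the primary efficacy endpoint". Under protocol 9.3.2.1 that means counts and percentages with Clopper-Pearson intervals, Boschloo's test, and a Miettinen-Nurminen interval for the difference.

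The current SAP treats the same endpoints in three places:

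- **SAP 3.7 and Table 5.** If the primary p-value is below 0.05 in a group of a cohort, "we will test the secondary efficacy endpoints in three reversal target clusters in parallel as shown in" Table 5. The clusters are the 120%, 115% and 110% targets, each tested in fixed sequence.
- **SAP 4.6.2.** The first two endpoints get counts and percentages. For the others: "No statistical analysis will be performed for the remaining secondary efficacy endpoints".
- **SAP 4.11.** This lists the reduction in 4.6.2 as a change from the protocol and describes it as a simplification. It does not mention 3.7 or Table 5.

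SAP Section 1 says the study was terminated after a lack of efficacy relative to placebo was seen in Group 1 of Cohorts 1 and 3, and that the scope of analysis was revised. SAP 3.2 says the sponsor was unblinded to individual assignments. SAP 4.6.3 keeps counts and percentages at each single timepoint, including 15 and 30 minutes, at all three thresholds.

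**The concern.** There are two problems. First, pre-specified secondary results were removed once outcomes were known, and 4.11 gives no reason specific to these endpoints. The endpoints removed are all those that describe early, lasting reversal. SAP 3.7 says a goal of the study is to verify the dose and the endpoints for later evaluations, and six of the eight candidate endpoints will have no result to inform that choice.

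Second, 3.7 and Table 5 were not brought into line with 4.6.2. In a cohort with a positive primary, one section would call for tests that the other rules out.

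**Working it through.** **1. The plan's own figures.** The inputs are in SAP 3.4: "Assuming true response rates for the primary efficacy endpoint of 78% and 5% in the first active dose group and the placebo group", and "18 subjects with a 2:1 randomization ratio will have 91% power at 0.05 two-sided significance level based on the Boschloo's test". That is 12 against 6 subjects. Power is the sum over a and b of Bin(a; 12, 0.78) × Bin(b; 6, 0.05) × 1[p(a,b) < 0.05]. Here p(a,b) is the Boschloo p-value: Fisher's p as the ordering statistic, maximised over the common proportion.

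- Group 1: 90.9% with two-sided Fisher ordering (91.7% if the one-sided p-value is doubled), against 91% stated.
- Group 2, 66% against 5% with 12 per arm: 94.1%, against "12 subjects in each group will have 94% power".

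Both reproduce. They bear on this point only by fixing the target sizes and by showing what opens the Table 5 gate: for example, at least 6/12 against 0/6, or at least 9/12 against 1/6.

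**2. What is kept and what is dropped.** Numbering follows SAP 3.1.2 and treatment follows SAP 4.6.1 and 4.6.2.

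| Sustained to 6 h from | ≤120% of BL | ≤115% of BL | ≤110% of BL |
|---|---|---|---|
| 1 hour | primary: full analysis | no. 1: counts, % | no. 2: counts, % |
| 30 minutes | no. 3: none | no. 4: none | no. 5: none |
| 15 minutes | no. 6: none | no. 7: none | no. 8: none |

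- Table 5 holds 2 + 3 + 3 = 8 endpoints; 4.6.2 keeps 2 and drops 8 − 2 = 6.
- Over Cohorts 1 and 3: 8 × 2 = 16 results, of which 6 × 2 = 12 have no summary (12/16 = 75%) and 2 × 2 = 4 have no interval.

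**3. What the retained tables determine.** By the responder rule in SAP 3.6, a 1-hour responder meets the threshold at 1, 3 and 6 hours. Applied in the same way, a 30-minute responder must also meet it at 0.5 hour, and a 15-minute responder at 0.25 and 0.5 hour. At one threshold and in one arm of size N, let R60, R30 and R15 be the sustained counts and X30 the single-timepoint count at 30 minutes. Then:

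- R15 ≤ R30 ≤ R60, so the kept 1-hour counts are upper bounds.
- max(0, R60 + X30 − N) ≤ R30 ≤ min(R60, X30).

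Illustration with assumed counts: N = 12, R60 = 6, X30 = 6. The lower limit is max(0, 6 + 6 − 12) = 0 and the upper limit is 6. If placebo has R60 = 0 of 6, its R30 is exactly 0. The arm difference could then lie anywhere from 0/12 = 0% to 6/12 = 50%. The bounds are tight only at the extremes, such as R60 = 0.

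**4. Interval widths.** Clopper-Pearson limits are the 0.025 quantile of Beta(x, n−x+1) and the 0.975 quantile of Beta(x+1, n−x).

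- 6/12: 21% to 79%.
- 0/6: 0% to 1 − 0.025^(1/6) = 46%.

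These are assumed counts at the target sizes of 12 and 6, not trial results. SAP Section 3 analyses the available data and gives no actual numbers.

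**The case against.** The case for leaving the SAP as it stands has several sound parts.

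- **The change is disclosed.** Protocol 9.3.1 asks that deviations from planned analyses be noted, and 4.11 notes this one in terms that match 4.6.2. A reader might infer that nobody can tell which section governs; 4.11 makes it evident that 4.6.2 does.
- **SAP 3.7 looks like carried-over text.** The SAP also keeps the Group 2 power statement, the total of about 108 subjects and a dose-proportionality comparison, although no Group 2 will be enrolled.
- **The tests are conditional.** They follow only if the primary p<0.05. Given the stated lack of efficacy, few or no p-values are likely to be lost. The documents give no p-value, so an open gate cannot be excluded.
- **SAP 3.6 is not a second contradiction.** Its sentence "The secondary efficacy endpoints will be analyzed in the same manner" might be taken as a promise of tests. It stands under missing data and is best read as the rule for responder status.
- **Early results remain.** A reader might infer that the trial will say nothing about reversal at 15 or 30 minutes. SAP 4.6.3 keeps those counts, with WBCT summaries and plots by arm.
- **Brevity is reasonable** for a terminated study.

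These points narrow the concern without removing it. Disclosure does not supply the missing results. The protocol's descriptive counts and intervals do not depend on the gate. Separate timepoint percentages do not give each subject's joint status. SAP Section 1 mentions by-subject listings in general, but a reader working from a listing is no substitute for a specified summary.

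**Conclusion.** The point holds as a change that should be made; neither the primary analysis nor subject safety is affected. Six protocol-planned sustained endpoints have no summary in either analysed cohort (12 of 16 results), two have counts without intervals (4 of 16), and 3.7 with Table 5 does not match 4.6.2. The main loss is descriptive: the number reversed from 30 or 15 minutes through 6 hours in each arm, and the difference between arms.

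A reader might go further and infer selective reporting in the drug's favour. The documents do not support that. The dropped endpoints are the stricter, nested ones, nothing shows that omitting them helps ciraparantag, the primary keeps its test and intervals, and the cut is declared. What the documents do show is that it was made after results were known.

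The counts rest on the SAP's numbering and on Cohorts 1 and 3 being the only ones analysed. The nesting rests on the SAP 3.6 responder rule. The interval widths rest on assumed counts at target sizes.

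**What to change.** - **SAP 4.6.2:** for each of the eight secondary endpoints, in Cohorts 1 and 3, report n/N and percentage by arm with the Clopper-Pearson 95% interval, and the arm difference with the Miettinen-Nurminen 95% interval. Use the primary-endpoint program and label the results descriptive.
- **SAP 3.7 and Table 5:** state that Boschloo p-values for secondary endpoints are produced, in the Table 5 order, only in a cohort whose primary p<0.05, and that otherwise the scheme is not applied.
- **SAP 4.11:** amend the secondary-endpoint entry to match, and say that this scope was settled after results were known.

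The cost is SAP wording and one further table per cohort, from data and code already needed for the primary endpoint. The report becomes slightly longer; no new data are required.

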### **4.6.3 Tertiary Efficacy Endpoints**

The tertiary efficacy endpoints are as stated in [Section 3.1.3](#). These endpoints are exploratory in nature and are intended to characterize effects at each of the specified WBCT assessment timepoints.

The first four sets of tertiary efficacy endpoints, achieving a WBCT  $\leq 120\%$ ,  $\leq 115\%$  or  $\leq 110\%$  of BL at each of the planned post-BL WBCT assessment timepoints by coagulometer or the manual method, will be tabulated by counts and percentages and no

statistical testing will be performed.

The fifth sets of tertiary efficacy endpoints will be summarized by cohort and treatment using descriptive statistics. The sixth sets of tertiary efficacy endpoints will not be analyzed.

The observed WBCT value, change from baseline, percentage change from baseline, and WBCT as percent of BL assessed using coagulometer or manual method will be summarized and plotted by time point and treatment group for each cohort.

#### **4.6.4 Correlations of WBCT Results between Coagulometer and Manual Method**

Correlation between WBCT as percent of BL obtained with coagulometer and manual method will be analyzed by fitting a simple linear regression model between these two sets of results. The value of  $R^2$  will be presented. Scatter plot of coagulometer results vs. manual method results will be provided along with the regression line.

#### **4.7 Safety Analysis**

All safety summaries will be presented by cohort and treatment (i.e., ciraparantag doses and PBO), and also by pooled ciraparantag vs pooled PBO across cohorts.

##### **4.7.1 Study Product Exposure**

Study drug and anticoagulants administration will be listed by subject, indicating date and time of drug dose. The study drug administration diary entries will be listed for all subjects, as applicable. A summary of the exposure will be presented, including total dose (mg) of anticoagulant (apixaban or rivaroxaban) administered, total number of anticoagulant doses taken, compliance of anticoagulant (%), and number of subjects who received the planned ciraparantag / PBO dose.

##### **4.7.2 Adverse Events**

All AEs and SAEs will be coded using the Medical Dictionary for Regulatory Activities (MedDRA) Version 23.0 or later. Treatment-emergent AEs (TEAEs) are defined as those AEs with onset on or after the start of double-blind study drug administration (ciraparantag or PBO) or any adverse event already present at the start of double-blind study drug administration that worsens in severity. For AEs with missing start dates, the AE will be considered treatment-emergent unless there is additional information indicating that the AE started prior to study drug administration.

The number and percentage of subjects with at least one TEAE, at least one serious TEAE, at least one ciraparantag or PBO related TEAE, and at least one TEAE leading to study withdrawal, and at least one TEAE of Special Interest (AESI) will be presented by

cohort and treatment group. AEs that are related or possibly related to study drug, or for which the relationship is missing, will be considered study drug related. AEs of Special Interest include the following categories based on selected preferred terms:

- Altered sensation of temperature: Flushing, Hot flush, Feeling hot, Feeling cold, Feeling of body temperature change, Chills
- Paresthesia or Dysgeusia: Paraesthesia, Dysgeusia

TEAEs, serious TEAEs, TEAEs leading to study discontinuation, ciraparantag or PBO related TEAEs, and TEAE of Special Interest will be summarized by SOC and PT for each cohort and treatment group, and also by pooled ciraparantag vs pooled PBO across cohorts. The same summary will also be performed by PT only with decreasing frequency based on the pooled ciraparantag group.

TEAEs will also be summarized by severity, by relationship to anticoagulants, and by relationship to ciraparantag or PBO. If the same AE (SOC/preferred term) is reported more than once for the same subject, the highest severity grade or the strongest relationship to treatment will be counted in the summary table.

All of these AE analyses will be performed on the Safety Population.

AEs with onset on or after the first dose of anticoagulant but prior to the double-blind study drug administration will be considered non-treatment emergent. The numbers and percentages of subjects having such a non-treatment-emergent AE and a non-treatment-emergent SAE in each SOC and Preferred Term will be summarized for the anticoagulant population by cohort and overall across cohorts.

Separate listings will be provided for deaths, SAEs, and AEs leading to study withdrawal. By-subject AE listings will be provided.

#### **4.7.3 Clinical Laboratory Assessments**

All quantitative laboratory test results, including serum chemistry, hematology, and prothrombotic markers, will be summarized by cohort, treatment, parameter, and time point using descriptive statistics for subjects in the Safety Population. The change from BL to each post-ciraparantag/PBO dose time point will also be summarized. Urinalysis results will be tabulated by counts and percentages. These will also be summarized by pooled ciraparantag vs pooled PBO across cohorts.

Laboratory values will be reported in Système International units.

Clinically notable (CN) laboratory values will be determined based on the criteria in [Appendix 1](#). The number and percentage of subjects with at least 1 CN laboratory value at any post-baseline timepoint will be summarized by cohort, treatment, and parameter.

Percentages for each laboratory test will be based on the number of subjects with at least one post-baseline evaluation for the specific parameter.

In addition to the CN summary, the number and percentage of subjects meeting each of the following criteria at any post-baseline timepoint will be summarized by cohort, treatment, and parameter:

- AST >3 x ULN, >5 x ULN and >10 x ULN
- ALT >3 x ULN, >5 x ULN and >10 x ULN
- Total bilirubin >1.5 x ULN and >2 x ULN

Laboratory values will be listed for each subject. Laboratory values outside normal limits will be identified in the subject data listings with flags for low (L) and high (H) as will laboratory values that meet the CN thresholds. A separate listing will be provided of subjects with values for a laboratory parameter noted as CN.

